3.16.3.1.1. Weeks 4, 8, 12, 16, 20, and 24 (Visits 14 Through 19)

During the study drug treatment period, patients will return to the study center once every 4 weeks (± 7 days) thereafter (relative to DoR/baseline) for administration of study drug and assessments until the end of the treatment period (week 24 or early withdrawal).

The following procedures/assessments will be performed before administration of study drug unless otherwise indicated:

- Perform urine pregnancy testing at weeks 4, 8, 12, 16, 20, and 24 or early withdrawal
- Perform hematology tests (CBC with differential) at weeks 4, 8, 12, 16, 20, and 24 or early withdrawal
- Perform serum chemistry tests (weeks 12 and 24 or early withdrawal) (a sample for CPK measurement only will also be collected on weeks 4, 8, 16, and 20).
- Perform brief physical examination at weeks 4, 8, 12, 16, 20, and 24 or early withdrawal
- Perform vital signs measurements (includes systolic and diastolic blood pressure, pulse, body temperature, and respiratory rate) at weeks 4, 8, 12, 16, 20, and 24 or early withdrawal
- Measure height and weight (week 24 or early withdrawal) for patients 12 to <18 years of age
- Measure weight (week 24 or early withdrawal) for adult patients
- Perform ECG (week 24 or early withdrawal)
- Perform adverse event inquiry
- Complete asthma-specific tests
 - Provide and collect PEF meter (week 24 or early withdrawal)
 - Provide/collect electronic asthma control diary; reinforce diary and PEF compliance (weeks 4, 8, 12, 16, 20, and 24 or early withdrawal)
 - OCS reduction attempts (weeks 4, 8, 12, 16, and 20)
 - Pre-bronchodilator spirometry (weeks 4, 8, 12, 16, 20, and 24 or early withdrawal)
 - Post-bronchodilator spirometry (weeks 4, 12, 20, and 24 or early withdrawal)

- AQLQ +12 (weeks 4, 8, 12, 16, 20, and 24 or early withdrawal) (may be completed after study drug administration during the 1-hour observation period)
- ACQ-6 (weeks 4, 8, 12, 16, 20, and 24 or early withdrawal) (may be completed after study drug administration during the 1-hour observation period)
- Collect blood for asthma biomarker analysis (week 24 or early withdrawal)
- Assess CAEs and related health care utilizations
- Collect blood for serum reslizumab concentration determination (PK assessment) (weeks 4, 8, 12, 16, 20, and 24 or early withdrawal)
- Collect blood sample for immunogenicity assessment (weeks 4, 8, 12, and 24 or early withdrawal)
- [REDACTED]
- [REDACTED]
- Complete EQ-5D (week 24 or early withdrawal) (may be completed after study drug administration during the 1-hour observation period)
- [REDACTED]
- Complete SGRQ (weeks 12 and 24 or early withdrawal) (may be completed after study drug administration during the 1-hour observation period)
- Record any concomitant medications
- Investigational product (IP) administration (weeks 4, 8, 12, 16, and 20)
- Assess any OCS withdrawal effects (based on investigator’s assessment)

Additionally, the following procedures/assessments will be performed during and after administration of study drug:

- Patients will be observed for 1 hour after study injection.
- Evaluation of injection site for reaction at approximately 1 hour after dosing using the injection site CRF. Clinically significant injection site reactions should be recorded as an adverse event.
- If, during post-study drug observation, the patient develops clinical symptoms, vital signs should be collected. The patient should be assessed for anaphylaxis/hypersensitivity reactions as detailed in Section 7.1.7.

Remind the patients that they will receive a post-injection symptom inquiry via the eDiary.

3.16.4. Procedures After Study Drug Treatment

Patients who participate in the study in compliance with the protocol for at least 24 weeks of double-blind treatment will be considered to have completed the treatment period. Patients who complete the follow-up visit (approximately week 32) will be considered as having completed the study. See Section 12.4 for the definition of the end of the study.

Patients who discontinue the study drug prematurely must be encouraged to continue to attend the regular scheduled visits and complete the prescribed safety and efficacy evaluations through the EOT/early withdrawal visit and the follow-up visit, if at all possible (see Section 4.5).

Patients who both discontinue the study drug and also withdraw from the study should have final evaluations performed on the last day they receive the study drug or as soon as possible thereafter. Patients should also return for the follow-up visit and procedures if at all possible (see Section 4.5).

Procedures for patients who withdraw prematurely from the study are described in Section 4.5. Following termination of the study, patients should be treated according to the standard of care, and as guided by the principal investigator.

Patients with ongoing adverse events or clinically significant abnormal laboratory test results (as interpreted by the investigator) will be monitored as described in Section 7.1.2 and Section 7.3, respectively.

The following procedures/assessments will be performed at the follow-up visit (EOT + 8 weeks \pm 7 days [visit 20]):

- Hematology tests (CBC with differential)

- Collect blood for serum reslizumab concentration determination (PK assessment)
- Collect blood sample for immunogenicity assessment
- Concomitant medication inquiry
- Adverse event inquiry
- Perform urine pregnancy test

The following procedures/assessments will be performed at the late follow-up visit (EOT + 24 weeks \pm 14 days [visit 21]):

- Collect blood for serum reslizumab concentration determination (PK assessment)
- Collect blood sample for immunogenicity assessment

3.16.5. Unscheduled Visits

An unscheduled visit may be performed at any time during the study at the subject's request or as deemed necessary by the investigator. The date and reason for the unscheduled visit as well as any other data obtained (eg, adverse events, concomitant medications and treatments, and results from procedures or tests) will be recorded on the CRF and within the patient's source notes.

Procedures performed during unscheduled visits include the following:

- Perform concomitant medication inquiry
- Perform vital signs measurements
- Perform adverse event inquiry

Clinical Study Protocol with Amendment 02

- Perform evaluation of any signs and/or symptoms of adrenal insufficiency (OCS withdrawal effects)
- Perform study compliance review

Other procedures may be performed at the discretion of the investigator.

4. SELECTION AND WITHDRAWAL OF PATIENTS

Prospective waivers (exceptions) from study eligibility criteria to allow patients to enter a study are not granted by Teva (see Section 11.1.2).

4.1. Patient Inclusion Criteria

Patients may be included in the study only if they meet all of the following criteria:

- a. The patient is male or female, 12 years of age and older, with a previous diagnosis of asthma. Patients 12 to <18 years of age are excluded from participating in South Korea, the Netherlands, and Argentina, and patients 66 years of age and older are excluded from participating in South Korea.
- b. Written informed consent is obtained. During the screening period, a signed and dated informed consent form (ICF) (and an assent form for children 12 through <18 years of age in accordance with local standards) will be obtained before a diagnosis of asthma is confirmed on the basis of patient history and by demonstration of airway reversibility.
- c. The patient continues to require an average daily maintenance dose of OCS for asthma of between 5 and 40 mg of prednisone or equivalent during the 3 months before screening. Patients on an OCS dose of >40 mg at screening who the investigator believes may be able to decrease OCS dose to ≤40 mg during the optimization period may also be enrolled. Note: every-other-day dosing that is within this daily average (ie, 10 to 80 mg) is allowed.
- d. The patient has a documented blood eosinophil level of at least 300/μL during the previous 12 months while on at least medium total daily dose of ICS based on Global Initiative for Asthma 2016 clinical comparability table ([Appendix A](#)), or ≥300/μL at screening while on chronic OCS or that becomes manifest during the OCS optimization period or at the week -2 visit (end of optimization period/beginning of run-in period).
- e. The patient has required at least 880 μg of inhaled fluticasone propionate or equivalent daily PLUS another controller(s) (eg, LABA, long-acting anti-muscarinic antagonist, leukotriene inhibitor, or theophylline) or documented intolerance to another controller for at least 6 months before the screening visit. For a fixed-dose ICS/LABA preparation, the highest labeled dose in that region will satisfy this criterion. For patients 12 through <18 years of age, the ICS dose must correspond to at least a medium total daily ICS dose. Note: the dose and regimen of asthma controllers and any allergen immunotherapy should have been stable during the 30 days before signing the Informed Assent Form/ICF.
- f. The patient has FEV₁ reversibility of at least 12% after administration of inhaled reliever medication according to the standard American Thoracic Society (ATS) or European Respiratory Society (ERS) protocol. Given the refractory nature of the disease in this population and the influence of high background controller medications on reversibility testing, documented FEV₁ reversibility of 12% or a

- provocation concentration producing a 20% fall in FEV₁ for methacholine of ≤ 8 mg/mL within 24 months of the screening visit, and performed according to the standard ATS/ERS procedures, would fulfill this criterion. Patients may be screened again if they did not meet spirometry/reversibility criteria initially. The duration between the date of Screen Failure and the re-screening must be >30 days.
- g. Females of childbearing potential (not surgically sterile by hysterectomy, bilateral salpingectomy, bilateral oophorectomy, or 2 years postmenopausal) must have exclusively same-sex partners or use medically acceptable methods of birth control and must agree to continue use of this method for the duration of the study and for 5 months after the last study drug dose. Acceptable methods of birth control include intrauterine device, systemic hormonal contraceptive (oral, implanted, transdermal, or injected), barrier method with spermicide, abstinence, bilateral fallopian tube occlusion, and partner vasectomy.
 - h. The patient must be willing and able to comply with study restrictions, willing and able to perform requisite procedures and remain at the clinic for the required duration during the study period, and willing to return to the clinic for the follow-up evaluation as specified in this protocol.
 - i. Except for the OCS, which will be adjusted per protocol, the patient must maintain his/her usual asthma controller regimen without change throughout the screening, optimization, run-in, and treatment periods.

4.2. Patient Exclusion Criteria

Patients will be excluded from participating in this study if they meet any of the following criteria:

- a. The patient has any clinically significant, uncontrolled medical condition (treated or untreated) that would interfere with the study schedule or procedures and interpretation of efficacy results or would compromise the patient's safety.
- b. The patient has another confounding underlying lung disorder (eg, chronic obstructive pulmonary disease, interstitial lung disease, bronchiectasis eosinophilic granulomatosis with polyangiitis [also known as Churg-Strauss syndrome], or allergic bronchopulmonary aspergillosis).
- c. The patient has a known hypereosinophilic syndrome.
- d. The patient has a history of any malignancy within 5 years of the screening visit, except for treated and cured nonmelanoma skin cancers.
- e. The patient is pregnant or intends to become pregnant during the study or within 5 months from last dose of study drug or is lactating. Any woman becoming pregnant during the study will be withdrawn from the study.
- f. The patient required treatment for an asthma exacerbation within 4 weeks of screening.
- g. The patient is a current smoker (ie, has smoked within the last 6 months before screening) or has a smoking history ≥ 10 pack-years.

- h. The patient is currently using any systemic immunosuppressive or immunomodulatory biologic agents (eg, anti-immunoglobulin E mAb or other mAb [eg, mepolizumab] or soluble receptor) or nonbiologic (eg, methotrexate, cyclosporine), except maintenance OCS for the treatment of asthma. Previous use of such agents that occurred >5 half-lives from the screening visit may be allowed, if approved by the medical monitor.
- i. The patient participated in a clinical study within 30 days or 5 half-lives of the investigational drug before screening, whichever is longer.
- j. The patient was previously exposed to benralizumab within 12 months of screening.
- k. The patient was previously exposed to reslizumab.
- l. The patient has a history of immunodeficiency disorder including HIV.
- m. The patient has current suspected drug and/or alcohol abuse.
- n. The patient has had an active helminthic parasitic infection or was treated for one within 6 months of screening.
- o. The patient has a history of allergic reactions or hypersensitivity to any component of the study drug.
- p. The patient has a history of latex allergy. (The current prefilled syringe device has a natural rubber component to the needle shield.)

4.3. Justification for Key Inclusion and Exclusion Criteria

The inclusion and exclusion criteria select for an OCS-dependent asthma phenotype with elevated eosinophils and that is likely to benefit from a targeted therapy such as reslizumab, while ensuring that enrolled patients are of sufficient health quality to ensure that participation in this study will not put them at unnecessary risk.

4.4. Randomization criteria

After completion of the optimization/run-in period, patients may continue in the study if they meet all of the following criteria:

- a. The patient must be using an average daily dose of no less than 5 mg of prednisone after OCS optimization. A patient requiring less than 5 mg of prednisone to maintain control should not be randomized.
- b. The patient must be using an average daily dose of no more than 40 mg of prednisone after OCS optimization. A patient requiring more than 40 mg of prednisone to maintain control should not be randomized.
- c. The patient should not have had an asthma exacerbation during the run-in period, defined as requiring a burst of systemic corticosteroid for an asthma worsening (injection, or if oral, at least a doubling from the current OCS dose for at least 3 days); an asthma-specific hospital admission; or an asthma-specific emergency department visit.

- d. The patient must have completed at least 4 days of diary entries (or any combination of 4 morning and 4 evening recordings) during the last 7 days of the run-in period.

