3.1.4. Treatment Period

Patients continuing to meet eligibility criteria on the day of randomization (day 1, week 0) will be randomly assigned in a 1:1 ratio to receive placebo or reslizumab 110 mg once every 4 weeks

through week 20, followed by an EOT visit at week 24. Patients will begin treatment on day 1 after completing baseline assessments, and they will return to the research facility for outpatient visits every 4 weeks through week 24 (EOT visit) for safety, PK, PD, immunogenicity, and efficacy assessments as applicable.

During the treatment period, the patient will continue his/her usual non-OCS background asthma medication without change; the OCS dose will be tapered per protocol. The treatment periods consist of the following:

- **Induction:** The minimally effective dose of OCS will be maintained, unchanged, during the first 4 weeks of the treatment period to allow sufficient time for any potential treatment effect to become established.
- **OCS reduction:** The minimally effective OCS dose will be reduced per protocol at scheduled clinic visits from the beginning of week 5 (ie, end of the induction period) through week 20, as long as all 5 criteria in [Table 2](#) are met and there are no clinical manifestations of adrenal insufficiency. These 5 eligibility criteria assure that the patient's asthma control is not significantly worsened compared to baseline. The last possible dose reduction can occur at week 20. The algorithm for OCS reductions during the treatment period is given in [Table 3](#).

If the OCS dose could not be decreased, it should be held constant, or may be increased to a previous level, at the investigator's discretion, until dose reduction criteria are met.

- **Maintenance:** OCS will be held stable from week 20 through EOT at week 24.

Table 2: Eligibility Criteria for Scheduled Oral Corticosteroid Reductions During the Treatment Period (Must Meet All)

1	Forced expiratory volume in 1 second (FEV ₁) ≥80% of baseline ^a
2	AM PEF ≥80% of baseline mean AM PEF on at least 5 of the 7 days preceding the visit
3	Mean nighttime awakenings due to asthma requiring rescue inhaler over the preceding 7 days ≤ 150% increase over the baseline period
4	Reliever bronchodilator inhaler use does not exceed 150% of the baseline inhaler use per 24 hours on more than 2 of the preceding 7 days
5	No increase in OCS dose since the previous visit ^b

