4.2.2. Diary

Baseline for diary variables (eg, PEF, total asthma symptom score, total reliever use) will be derived as the average of the run-in values over the 7 days preceding baseline/DoR (see [Table 6](#) for the definition of analysis days for diary data). At least 4 out of the 7 expected measurements need to be recorded for each diary variable; otherwise the baseline value for that variable will be treated as missing.

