For summaries of diary data (eg, rescue medication use, asthma symptom score), the day used for analysis will consist of the evening assessment for the day and the morning assessment for the following day, as illustrated in Table 6. Weekly average data will be generated using 7-day window intervals derived based on these analysis days.

Table 6: Definition of Analysis Days for Diary Data

Study Period	Diary Day	Study Day ^a	Time Point
Baseline	Day -7	-7	PM
		-6	AM
	Day -6	-6	PM
		-5	AM
	Day -5	-5	PM
		-4	AM
	Day -4	-4	PM
		-3	AM
	Day -3	-3	PM
		-2	AM
	Day -2	-2	PM
		-1	AM
	Day -1	-1	PM
		1 (pre-dose)	AM
Treatment	Day 1	1	PM
		2	AM
	Day 2	2	PM
		3	AM
	PM
		..	AM
	Day 167	167	PM
		168	AM

^a Study Day 1 denotes the first dose of study drug; Study Day -1 is the day prior to the first dose of study drug.

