6.4.9. Asthma Control Diary

6.4.9.1. Variable Definition

6.4.9.1.1. Asthma symptom scores

The asthma symptom score will be determined every morning and evening by the patient and recorded in the daily asthma control diary. The asthma symptom score is used to measure how much patients are bothered by their asthma symptoms. Asthma symptom score will be rated on a scale, with higher scores indicating more severe symptoms. The daytime asthma symptom score (range: 0-5) will be assessed in the evening and indicate how the patient felt earlier that same day. The nighttime asthma symptom score (range: 0-4) will be assessed in the morning and indicate how the patient felt during the previous night. Total asthma symptom score (range: 0-9) will be derived as the sum of the daytime and nighttime symptom scores.

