6.4.9.1.2. Total reliever use

The number of times SABA reliever therapy is used will be recorded by the patient, once in the morning and once in the evening. Total reliever use will be derived as the sum of the morning and evening counts.

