6.4.9.2. Analysis

Compliance with the daily diary assessments will be derived for each patient as an additional measure of protocol adherence. A diary compliant day will be defined as a day with non-missing values for all diary assessments, including AM/PM asthma symptom score, AM/PM reliever use, AM/PM PEF, and nighttime awakenings. Diary compliance will be derived as a percentage over the treatment period:

- $\text{Diary compliance (\%)} = 100 \times (\text{total number of diary compliant days} / \text{total number of days during the treatment period})$

The treatment period for diary compliance extends from the first day of study drug to the last day of study drug. Note that, in this analysis, missing data will be treated as non-compliant (eg, if compliance cannot be assessed for a given day due to missing data, then the day will not be counted as a diary compliant day).

PEF measurements collected in the morning and in the evening will be summarized separately. Asthma symptoms collected in the morning and in the evening will be summed to derive a total

daily symptom score. Total reliever use will be derived as the sum of the morning and evening counts.

A weekly average of the daily diary measures (AM/PM PEF, total asthma symptom score, and total reliever use) will be derived (see [Table 6](#) for the definition of analysis days for diary data). The average will be calculated as the sum of all values divided by the number of non-missing assessments. There will be no imputation of missing data. At least 4 of the 7 measurements need to be recorded for a week to be included in the analysis; otherwise the week will be treated as missing.

Nighttime awakenings will be derived and analyzed as a percentage over the treatment period, derived as:

$$\text{Awakening-free nights (\%)} = 100 \times (\text{total number of awakening-free nights} / \text{total number of days during the treatment period})$$

The treatment period is defined in [Section 6.4](#). Note that missing data will be treated as non-responders in this analysis (eg, if response for nighttime awakenings is missing for a given day, then the day will not be counted as an awakening-free night).

Summary statistics of actual values and change from baseline to each week will be provided by treatment group.

Analysis of the change from baseline to each week will use a similar MMRM model as described in [Section 6.4.3.2](#) with the exception of inclusion of sex and height in the model.

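### Protocol 4.4(d) does not require evening and morning diary entries to pair, so an eligible patient can lack the SAP baseline for total symptom score and total reliever use

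*Protocol*

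**What the plan says.** - Protocol 4.4(d) and the synopsis: "The patient must have completed at least 4 days of diary entries (or any combination of 4 morning and 4 evening recordings", within the last 7 days of run-in. Mornings and evenings are counted separately.
- SAP 4.2.2, which points to Table 6 for the days: "At least 4 out of the 7 expected measurements need to be recorded for each diary variable". When a patient falls below that threshold, the SAP drops the value: "otherwise the baseline value for that variable will be treated as missing".
- SAP 4.5: "the day used for analysis will consist of the evening assessment for the day and the morning assessment for the following day". Table 6 therefore runs from the evening of study day -7 to the pre-dose morning of day 1, which makes seven evening-morning pairs.
- SAP 6.4.9.1.1: "Total asthma symptom score (range: 0-9) will be derived as the sum of the daytime and nighttime symptom scores". SAP 6.4.9.1.2: "Total reliever use will be derived as the sum of the morning and evening counts".
- SAP 6.4.9.2 applies the same 4-of-7 threshold to the weekly averages and adds: "There will be no imputation of missing data". SAP 4.4 likewise plans no estimation of missing values for these variables.
- SAP 6.4.9.2 analyses weekly change from baseline with the MMRM of 6.4.3.2, less sex and height. Baseline stays in that model as a covariate.
- SAP Table 13, the list of departures from the protocol's analyses, does not mention the diary rule.

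**The concern.** Both rules ask for 4 out of 7, so criterion (d) looks as if it secures the baseline that the SAP needs. They count different things. The protocol counts recordings, or days with entries; the SAP counts values of a variable on diary days that straddle midnight. For a variable that is the sum of an evening and the following morning, four of each need not give four sums.

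If they do not, a properly randomized patient has no baseline for total symptom score and total reliever use. Without it there is no change from baseline and no covariate value, so the patient drops out of both models. Missing baseline is fixed before randomization, so this costs patients and precision and does not in itself favour one arm. It is still a loss that the eligibility rule seems suited to prevent.

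**Working it through.** The plan gives no figure for this, so there is none to reproduce. The check is a count of patterns.

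**Inputs.** Seven diary days (SAP Table 6), each an evening plus the next morning. Minimum of 4 mornings and 4 evenings (Protocol 4.4(d)). At least 4 of 7 values needed (SAP 4.2.2). A total needs both halves (SAP 6.4.9.1.1 and 6.4.9.1.2, read with the no-imputation rule).

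**Guaranteed pairs.** With k evenings and l mornings on the 7 diary days, the smallest possible number of complete days is max(0, k + l - 7).
- 4 + 4: 8 - 7 = 1.
- 5 + 5: 10 - 7 = 3.
- To guarantee 4, k + l must be at least 11 of 14.

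Example: evenings on diary days -7 to -4 and mornings belonging to diary days -4 to -1 satisfy 4.4(d), but only diary day -4 is complete.

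**Share of patterns with fewer than 4 complete days.** Fix the evenings and place the mornings in every possible way.
- 4 + 4: patterns with j pairs number C(4,j) × C(3,4-j), that is 4, 18, 12 and 1 for j = 1, 2, 3 and 4, out of C(7,4) = 35. Short: 34/35 = 97.1%. Mean number of pairs: 80/35 = 2.3.
- 4 + 5: 6, 12 and 3 of 21 for j = 2, 3 and 4. Short: 18/21 = 85.7%.
- 4 + 6: 4 and 3 of 7 for j = 3 and 4. Short: 4/7 = 57.1%.
- 5 + 5: C(5,j) × C(2,5-j) gives 10, 10 and 1 of 21 for j = 3, 4 and 5. Short: 10/21 = 47.6%.
- 4 + 7, 5 + 6 and anything fuller: never short.

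**The four-days limb.** Read the days as calendar days -7 to -1, each with its own morning and evening. Days -7 to -4 recorded in full give three SAP pairs: evening -7 with morning -6, -6 with -5, and -5 with -4. The morning of day -7 lies outside Table 6 and the evening of day -4 has no partner. Over all 35 choices of four whole days, none gives 4 pairs if the day 1 morning is absent (3, 2, 1 and 0 pairs in 4, 18, 12 and 1 choices). If it is present, one choice does (days -4 to -1).

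**The window.** On the same calendar reading, 20 of the 35 choices of four mornings include the morning of day -7. That leaves 3 in the Table 6 window unless the day 1 morning is also recorded.

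**If half-days were counted as totals.** Take constant evening and morning values e and m, with 4 + 4 entries and one pair. All seven diary days then carry something, and their average is (4e + 4m)/7, or 4/7 of the true total e + m. The baseline would exist but be too low.

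**The case against.** The SAP nowhere says that a half-recorded day makes the total missing; that is an inference from the sum definition and the absence of imputation. This stands, and it makes the point partly one about an unstated rule. The other reading gives an understated baseline, so the rule needs stating either way.

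For reliever use, the sample diary in Protocol Appendix D asks for one daily puff total, where the SAP describes morning and evening counts. The sample is marked as reference only. If a single daily figure is what is collected, pairing does not arise for reliever use and only the symptom score is affected.

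The protocol gives no day numbers for the last 7 days of run-in, so the pre-dose morning of day 1 may be inside them. That would remove the window difference but not the pairing problem.

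Two stronger readings are tempting and are not supported.
- A reader might infer that 97% of patients at the minimum lose their baseline. The figure weights all patterns equally. Missed entries may cluster by day, which would keep pairs together, and the schedule has sites reinforce diary compliance at each optimization, run-in and treatment visit. The documents give no compliance figure, so the number affected could be close to zero.
- A reader might infer that the gap reaches the OCS taper, and through it the primary endpoint, because Table 2 criterion 4 requires that reliever use "does not exceed 150% of the baseline inhaler use per 24 hours" on more than 2 of the preceding 7 days. The Table 2 footnote defines its own diary baseline, the average over the 7 days before randomization, with no 4-of-7 minimum, no pairing and no set-to-missing rule. A patient without a SAP baseline can still have that one.

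**Conclusion.** The mismatch is in the current text and worth correcting, at modest weight. A patient can satisfy 4.4(d) with as few as 1 complete SAP diary day, and four full consecutive calendar days (-7 to -4) yield only 3. On the natural reading the patient then has no baseline for total symptom score or total reliever use and leaves both change-from-baseline models.

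This rests on two assumptions: a half-recorded day has no total, and reliever use is collected as separate morning and evening counts. On aligned diary days it can touch only patients with 10 or fewer of 14 entries.

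The consequence is confined to two other efficacy endpoints that carry no multiplicity control. AM and PM PEF are separate variables and need no pairing. The primary and secondary endpoints rest on OCS dose and exacerbations, and loss of control on FEV₁, ACQ-6 and exacerbations, so none of them uses these totals.

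**What to change.** Preferred: in SAP 4.2.2 and 6.4.9.2, derive each of the two totals as the mean of the available evening values plus the mean of the available morning values over the 7 diary days, each from at least 4 of 7 and otherwise missing. Apply it to baseline and weekly values alike. In Protocol 4.4(d), state that the 7 days are the Table 6 diary days -7 to -1, from the evening of day -7 to the pre-dose morning of day 1. With the windows aligned, 4.4(d) then guarantees what the baseline needs, provided each recording contains both items, and no patient is lost. The cost is one sentence in the protocol, a short SAP edit, one programming rule and a small change in how the totals are derived.

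Alternative: reword 4.4(d) and the synopsis to require 4 complete Table 6 diary days. This leaves the derivation alone but would exclude or delay a few patients with sparse diaries, and the SAP should still say how a half-recorded day is treated.

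Separately, the diary-baseline window in the Table 2 footnote (7 days before randomization) and the one in SAP Table 6 (through the morning of day 1) should be reconciled. How the OCS-reduction criterion itself is applied is for the sponsor to settle.
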